7.11.2.6 Normalization of WBC and Lymphocytes

White Blood Cell (WBC) count and lymphocytes counts will be performed at the Screening visit and any days the patient is hospitalized from Day 1 through Day 28 and at Day 90.

Normalization of WBC and lymphocyte count is defined as whether WBC and lymphocyte count results are normal or below normal or above normal ranges at available visits. A summary table and listing will be generated for normalization of WBC and lymphocytes.

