5.2.2 Secondary Endpoints

• Change in ordinal scale.

- All cause 28-day mortality.
- Number of patients with treatment-emergent serious adverse events or clinically significant adverse drug reactions (ADRs).
- Survival time and causes of death.
- Time to improvement in oxygenation (PaO₂/FiO₂ ratio, SpO₂/FiO₂ ratio and P(A-a)O₂ gradient).
- Rate of nosocomial infection (as determined by local institution practice).
- Duration of hospitalization.
- Number of patients requiring initiation of mechanical ventilation.
- Duration of invasive and non-invasive ventilation and/or supplemental oxygen.
- Time to normalization of WBC and lymphocytes.

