6.2 Randomization

Per Section 5.2 of the Study Protocol, randomization will be performed, using a 2:1 randomization ratio, with the strata defined as:

- investigational site,
- SOFA score (<6 versus ≥ 6)

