7.1 General Considerations

All safety analyses will be based on Safety Population; all efficacy analyses will be based on Modified Intent-to-Treat population, unless otherwise specified. Some specific sensitivity analyses of efficacy may be based on ITT and Per Protocol populations (for primary endpoints only). See Section 7.4 below for definitions of each analysis population.

All analyses will be considered as descriptive analyses. Derivation of two-sided 95% confidence intervals and p-values will be generated where applicable.

Time to event endpoints will be defined as the start date/time to the end date/time; censoring dates will be the last date/time the patient was determined to be event-free. Kaplan Meier methods will be used for time to event endpoint analyses; a log-rank test will be performed to compare the two survival curves. Timepoints estimates and median survival will be derived from the Kaplan Meier analysis. A Cox proportional hazards model may also be used to compare the two treatment arms using a hazard ratio.

Categorical endpoints will be calculated as the percentage of patients with the event, relative to the number of patients in a given analysis population (see Section 7.4). Stratified logistic regression approaches and/or repeated measures statistical approaches may be used to compare patients on the sargramostim and control arms, in addition to Fisher's Exact or Chi² tests (as appropriate). The randomization stratification factor for the baseline SOFA score (<6 versus \geq 6) will be considered for any stratified analysis.

Continuous endpoints will be summarized by n, means, medians, minimum, maximum, and 25th and 75th percentiles. Analysis of variance, analysis of covariance, and/or repeated measures statistical approaches may be used to compare patients on the sargramostim and control arms.

In the event that the underlying assumptions and/or distributions for a given statistical method are not satisfied, alternative statistical methods will be employed.

Additional exploratory analyses may be performed to evaluate the robustness and sensitivity of the study results, including but not limited to, additional evaluation of endpoints on other

analysis populations, subgroup analyses, treatment interactions, adjusted or stratified analyses, and/or alternative statistical methods.

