7.2 Sample Size

Approximately 120 patients will be randomized: of which 80 will receive sargramostim + SOC, and 40 patients who will receive SOC alone to evaluate the clinical efficacy and safety of sargramostim in patients with COVID-19 associated acute hypoxemia.

The sample size was based on practical and clinical considerations to ensure that the efficacy endpoints and safety profile could be appropriately evaluated and was not based on any statistical assumptions or hypotheses. As a result, the analyses of this study will be considered as descriptive analyses.

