7.4 Analysis Population

The following analysis populations will be used to summarize the results from this study.

- Safety Population includes all patients who received at least one dose of sargramostim and/or SOC based on actual treatment received. Patients who did not receive any study treatment (either sargramostim and/or SOC) will be excluded from Safety Population. All safety analyses will be based on the Safety Population.
- Intent-to-treat Population (ITT) includes all patients who were randomized, and analyzed per the treatment arm as randomized. Selected efficacy analysis (P(A-a)O₂ and intubation rate) may also be performed based on ITT population for the purpose of sensitivity, unless otherwise specified.
- Modified Intent-to-treat Population (MITT): a subset of the ITT population that received at least one dose of any study treatment (either sargramostim and/or SOC). Efficacy analyses will be based on the MITT Population.
- **Per Protocol Population (PP)** includes all patients who were randomized and received at least one dose of sargramostim and/or standard of care based on the treatment assigned

at randomization and meet the eligibility criteria of this study. Selected efficacy analyses may also be performed based on the Per Protocol Population, unless otherwise specified.

- If the ITT, and PP populations are identical, or less than 10% different compared to the MITT population, then the selected efficacy analyses may not be repeated across the ITT and PP analysis population.
- Enrolled Population includes all patients who were eligible and signed informed consent form (ICF).

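### SAP 7.11.2.6 defines WBC and lymphocyte normalization as range status at each visit, without conditioning on baseline, so the planned table cannot measure time to normalization

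*SAP*

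**What the plan says.** Section 5.2.2 lists the secondary endpoint "Time to normalization of WBC and lymphocytes". The only operational definition is in 7.11.2.6: "Normalization of WBC and lymphocyte count is defined as whether WBC and lymphocyte count results are normal or below normal or above normal ranges", applied at whatever visits are available. The output is equally brief: "A summary table and listing will be generated for normalization of WBC and lymphocytes". The section names no event, start time, at-risk group or test.

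Four other sections bear on the point:

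- **7.4 Analysis Population:** "Efficacy analyses will be based on the MITT Population". Section 7.1 expresses categorical endpoints as a percentage of the patients in the analysis population. Together these make the whole MITT population the default denominator.
- **7.1 General Considerations:** "Kaplan Meier methods will be used for time to event endpoint analyses; a log-rank test will be performed to compare the two survival curves". The rule covers time-to-event endpoints in general but supplies no event definition for this one.
- **7.1.2 Baseline Definition:** defines baseline, but 7.11.2.6 does not use it.
- **7.12.2 Laboratory data:** plans hematology values and changes from baseline by visit, with out-of-range values flagged in listings. It plans no cross-tabulation of baseline category against visit category.

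**The concern.** Normalization ordinarily means that an abnormal value becomes normal. The definition in 7.11.2.6 is a three-way classification of a result on a given day. A patient whose count was in range at entry and stays there falls in the same cell as a patient who entered out of range and recovered. Someone who was never abnormal has no time to normalization, so the 5.2.2 endpoint applies only to patients abnormal at baseline. The plan does not identify that group.

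What is at stake is how one secondary endpoint will be read. Under a heading of normalization, the percentage in range at a visit will probably be taken as the percentage who normalized, when part of it is simply the percentage who arrived normal.

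**Working it through.** **Is there a plan figure to reproduce?** No. Section 7.2 gives about 120 patients, "of which 80 will receive sargramostim + SOC, and 40 patients who will receive SOC alone", and says that the sample size "was not based on any statistical assumptions or hypotheses". No rate is stated for this endpoint, so every rate below is an assumption.

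**Formula.** Let f be the share normal at baseline, r the proportion of baseline-abnormal patients in range at the visit, and s the proportion of baseline-normal patients still in range. The displayed percentage normal is f·s + (1 − f)·r. With the same f in both arms (T sargramostim, C control), the displayed difference is

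f·(sT − sC) + (1 − f)·(rT − rC).

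If sT = sC, the first term vanishes and the difference shrinks by the factor 1 − f, the share abnormal at baseline.

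**Size of the shrinkage.** Assume r = 50% v 30% (a 20-point difference) and s = 100% in both arms:

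- f = 40%: 0.40 + 0.60 × 0.50 = 70% v 0.40 + 0.60 × 0.30 = 58%, displayed difference 12 points.
- f = 60%: 0.60 + 0.40 × 0.50 = 80% v 0.60 + 0.40 × 0.30 = 72%, displayed difference 8 points.
- f = 70%: 0.70 + 0.30 × 0.50 = 85% v 0.70 + 0.30 × 0.30 = 79%, displayed difference 6 points.

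**If baseline-normal patients do not behave alike.** At f = 60% the baseline-abnormal patients contribute 0.40 × 20 = 8 points. That is cancelled if baseline-normal patients stay in range 8 / 0.60 = 13.3 points less often on sargramostim than on control. With a larger gap the sign reverses. Simple dilution is therefore conditional.

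**Can a baseline column recover the missing information?** Suppose an arm goes from 60% normal at baseline to 72% at a visit. Two histories fit:

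- 12% of all patients move into range and none leave: 60 + 12 = 72.
- 30% move into range and 18% leave: 60 + 30 − 18 = 72.

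As 40% were abnormal at entry, normalization among them is 12/40 = 30% in one case and 30/40 = 75% in the other. Percentages by visit cannot tell these apart; a shift table can.

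**Baseline imbalance.** Assume no effect (r = 40% in both arms), s = 100%, and 65% v 50% normal at entry. The visit shows 0.65 + 0.35 × 0.40 = 79% v 0.50 + 0.50 × 0.40 = 70%, a 9-point gap. With 80 v 40 patients and 60% normal overall, the standard error of a baseline difference is √(0.6 × 0.4 × (1/80 + 1/40)) = 9.5 points. A gap of 15 points or more in either direction is thus 15/9.5 = 1.58 standard errors, with a chance probability of about 11%.

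**The case against.** The strongest reply is that 7.11.2.6 describes a status table and promises nothing more. A reader might infer that the plan counts baseline-normal patients as successes, or that a Kaplan-Meier curve would give them an event at the first visit. The SAP supports neither reading: it names no responder, success count or event, and a three-way status does not define one.

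A reader might also infer that an entry imbalance would pass for a treatment effect. Section 7.11.2 makes baseline a main timepoint for secondary measures, and counts are taken at screening, so a baseline column is likely. In the imbalance example it would show 65% v 50%, and the arm that started lower would be seen to gain more (70 − 50 = 20 points against 79 − 65 = 14).

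Nor can it be stated as fact that a real effect will be diluted. That depends on an unstated share normal at entry and on baseline-normal patients behaving alike in both arms. Sections 7.1 and 7.2 make all analyses descriptive, and 7.11.2.6 names no test, so no formal error rate is at stake. The mock tables are in a separate document and could already contain a shift layout; that cannot be judged from the SAP.

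These points limit the consequences and stand to that extent. They do not repair the definition. A baseline column exposes imbalance but, as shown above, does not separate patients entering the range from those leaving it. The changes from baseline in 7.12.2 do not do so either. A listing allows individual histories to be traced by hand, but that is not a planned summary.

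**Conclusion.** The point holds as a minor one. Followed as written, 7.11.2.6 yields the distribution of low, normal and high counts by visit. It does not show who normalized or when, which is what 5.2.2 asks. This conclusion rests on the text alone.

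The numerical consequence is conditional. A 20-point difference among baseline-abnormal patients would be displayed as 12 to 6 points if 40% to 70% are normal at entry, the share is equal in the two arms, and all of them stay normal. The SAP supplies none of these inputs, so neither the amount nor the direction of any distortion can be fixed from it. The harm is to the interpretation of one descriptive secondary endpoint.

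**What to change.** In 7.11.2.6:

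- Define normalization as the first post-baseline in-range value in a patient whose baseline value, as defined in 7.1.2, was out of range. Do this separately for WBC and for lymphocytes.
- Use baseline-abnormal patients as the denominator. Split them into low and high at baseline only where numbers allow.
- Add a baseline-by-visit shift table (low, normal, high) by arm for all MITT patients, so that those who leave the range are also visible.
- State how discharge and death before normalization are handled if the time to event is estimated. The default censoring rule in 7.1.5 speaks of patients who are alive.

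The cost is SAP wording and one table, from data already planned for collection. There are two downsides. The denominator falls: at 60% normal, 0.40 × 80 = 32 v 0.40 × 40 = 16 patients remain, and fewer in each low or high subgroup. The date of the first in-range value also depends on sampling, because counts are planned only at screening, on hospitalized days up to Day 28, and at Day 90. A patient discharged early with an abnormal count may have no further value until Day 90, and a single in-range value ignores later relapse. The text should acknowledge both limits.

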7.11.3 Exploratory Efficacy Evaluations

For exploratory efficacy measures. the main timepoints of interest for analyses are baseline, Days 6, 14, 28, where data are available, unless otherwise specified.

7.11.3.1 National Early Warning Score (NEWS-2)

The calculated total National Early Warning Score (NEWS-2) (See the scoring in Appendix D of the Study Protocol) will be summarized by treatment arm for each available timepoint of interest using descriptive analyses. Individual measures and overall score will be provided in patient data listing.

7.11.3.2 Sequential Organ Failure Assessment (SOFA)

Sequential Organ Failure Assessment (SOFA) are based on six different scores, including respiratory, cardiovascular, hepatic, coagulation, renal, and neurological systems. The overall calculated SOFA score will be summarized by treatment arm for each available timepoint.

Individual SOFA scores and its components such as the Glasgow Coma Score will be provided in a patient data listing.

The Glasgow Coma Score and the SOFA Scores are defined in Appendices A and B of the Study Protocol, respectively.

7.11.3.3 **ROX Index**

The ROX Index assessment is described in Appendix E of the Study Protocol.

ROX Index calculation = SpO₂/FiO₂ ratio/ Respiratory rate (breaths/min).

The ROX Index will be summarized by treatment arm . The ROX Index Score and its components will be listing by patient.

7.11.3.4 ARDS progression and Changes on Chest X-ray or CT

The exploratory endpoints of progression to ARDS and changes on chest x-ray or CT will be evaluated in terms of determining ARDS progression.

Chest X-ray or CT may be performed at the Screening visit, Treatment period Days 1-5, Posttreatment period at Day 6 or day of discharge (whichever is earlier), Days 7-27 (or until hospital discharge), Day 28, and Day 90.

Percentage of patients in whom ARDS or ARDS progression is documented post-baseline will be summarized. Potential available data sources for the diagnosis of ARDS/ARDS progression include adverse events, physical examination findings, imaging studies such as Chest X-ray, CT, treatment or study discontinuation reasons, etc.

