5.1 Study Objectives

The aim of the study is to determine if inhaled sargramostim, as an adjunct to institutional SOC, improves clinical outcomes in patients with COVID-19-associated acute hypoxemia.

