5.2.3 Exploratory Endpoints

- National Early Warning Score (NEWS-2).
- Sequential organ failure assessment (SOFA) scores.
- ROX Index.
- Progression to ARDS.
- Changes on chest X-ray or CT.

6 Study Design

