6.1 Study Design Overview

This study is a randomized two-arm open-label study. This Phase 2 study will randomize approximately 120 patients with COVID-19: of which 80 will receive sargramostim + SOC, and 40 patients who will receive SOC alone. Refer to Section 5.1 of the Study Protocol for a more detailed description of the study. Section 1 of the Study Protocol is a schematic of the study design.

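### As worded, the ARDS endpoint can count unchanged ARDS already present at entry as an event, if any patients enter with ARDS

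*SAP*

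**What the plan says.** - **Endpoint name.** SAP section 5.2.3 lists "Progression to ARDS" among the exploratory endpoints.
- **Event rule.** Section 7.11.3.4: "Percentage of patients in whom ARDS or ARDS progression is documented post-baseline will be summarized".
- **Sources.** The same section says: "Potential available data sources for the diagnosis of ARDS/ARDS progression include adverse events, physical examination findings, imaging studies such as Chest X-ray, CT". It adds discontinuation reasons and leaves the list open. Imaging is optional: "Chest X-ray or CT may be performed at the Screening visit", and likewise at later visits.
- **Denominator.** Section 7.11.3.4 gives none of its own, so section 7.1 governs: "Categorical endpoints will be calculated as the percentage of patients with the event, relative to the number of patients in a given analysis population". Section 7.4 supplies the population: "Efficacy analyses will be based on the MITT Population". Neither restricts it by ARDS status.
- **Entry population.** Section 5.1 asks whether treatment "improves clinical outcomes in patients with COVID-19-associated acute hypoxemia". The SAP does not say whether patients with ARDS at entry are excluded.
- **Baseline tables.** Section 7.7 names SOFA, the ordinal scale, NEWS-2 and COVID-19 diagnostic information, but not ARDS status.

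**The concern.** Progressing to ARDS means acquiring it after entry. The first limb of the rule in section 7.11.3.4 asks only that ARDS be documented after baseline. Followed literally, a patient who enters with ARDS and whose next film or examination note still records it is an event, although nothing has worsened.

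Two things would follow if such patients exist. First, both arms gain events that treatment could not have prevented, so a real difference in new ARDS looks smaller. Second, any chance difference between arms in entry ARDS passes into the result, and a reader could not see it because section 7.7 does not name ARDS status among the baseline summaries.

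**Working it through.** The SAP states no rate, effect size or power for this endpoint, so there is no figure to reproduce. The only document inputs are the arm sizes in section 6.1, "of which 80 will receive sargramostim + SOC, and 40 patients who will receive SOC alone" (80 + 40 = 120, ratio 2:1). All rates below are assumptions, used to show direction and range.

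**Illustration 1: entry ARDS adds events but no information.** Let b be the share with ARDS at entry, s the chance that it is noted again (the same in both arms), and p the true rate of new ARDS among the rest.

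Observed rate = b·s + (1 − b)·p, so the risk difference is multiplied by (1 − b).

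Assume p = 30% (control) and 15% (sargramostim): true difference 15.0 points, risk ratio 0.50.

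| b | Observed rates, s = 1 | Difference (points) | Risk ratio, s = 1 | Risk ratio, s = 0.5 |
|---|---|---|---|---|
| 0% | 30.0 vs 15.0% | 15.0 | 0.50 | 0.50 |
| 10% | 37.0 vs 23.5% | 13.5 | 0.64 | 0.58 |
| 20% | 44.0 vs 32.0% | 12.0 | 0.73 | 0.65 |
| 30% | 51.0 vs 40.5% | 10.5 | 0.79 | 0.71 |
| 50% | 65.0 vs 57.5% | 7.5 | 0.88 | 0.81 |

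Example, b = 20%, s = 1: control 0.20 + 0.80 × 0.30 = 0.44; sargramostim 0.20 + 0.80 × 0.15 = 0.32; ratio 0.32/0.44 = 0.73.

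**Illustration 2: entry-ARDS patients can also truly worsen.** Let q be the true rate of new or worsened ARDS in everyone, and r the chance that unchanged entry ARDS is noted again.

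Observed rate = b·(r + (1 − r)·q) + (1 − b)·q.

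With q = 15% vs 7.5% (ratio 0.50) and r = 0.7:
- b = 20%: 26.9 vs 20.5%, ratio 0.76
- b = 40%: 38.8 vs 33.4%, ratio 0.86
- b = 60%: 50.7 vs 46.4%, ratio 0.91

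At b = 0 the ratio is again 0.50.

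**Baseline imbalance with no treatment effect.** With q = 15% in both arms and r = 0.7, an imbalance Δ in entry ARDS produces a difference of 0.7 × 0.85 × Δ = 0.595·Δ. The standard error of Δ is √(b(1 − b)(1/80 + 1/40)), ignoring stratification.
- b = 10%: √(0.09 × 0.0375) = 5.8 points, so a one-standard-error imbalance gives about 3.5 points.
- b = 40%: √(0.24 × 0.0375) = 9.5 points, giving about 5.6 points.

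The true effect assumed in illustration 2 is 7.5 points.

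**What elsewhere in the SAP limits this.** Section 7.12.1 classes an adverse event that began before first dose as prior, and requires onset or worsening on or after first dose for an event to be treatment-emergent. That guards the adverse-event source. It does not reach imaging, examination findings or the open end of the source list.

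**The case against.** The strongest reply is that the literal reading is uncharitable. Section 7.11.3.4 is headed as ARDS progression, and its opening sentence says both exploratory endpoints will be judged in terms of progression. In that light the rule can be read as new ARDS, or worsening of existing ARDS. That reading is plausible and may be what was meant. But the operative sentence does not say it, and a programmer following that sentence would count re-noted ARDS.

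A reader might infer that naming progression alongside ARDS shows that the sponsor expects patients with ARDS at entry. The SAP does not support this. The phrase may simply be shorthand for the endpoint, or may cover worsening after onset on study. Eligibility is in the protocol, which is not at hand.

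Three further points stand in part:
- Randomization is stratified by SOFA score (section 6.2), which has a respiratory component (section 7.11.3.2). This probably reduces imbalance in entry ARDS, but does not remove it.
- A discontinuation attributed to ARDS is unlikely to be a mere repeat note.
- The dilution figures assume that re-documentation is equally likely in both arms. If treatment changed how long entry ARDS lasts, the percentage would mix resolution with progression instead, which is also not the named endpoint.

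**Conclusion.** The concern holds in conditional form. The stated rule, applied over all MITT patients, can score unchanged entry ARDS as an event. The protection in section 7.12.1 covers only the adverse-event source. If entry ARDS exists and is re-noted equally often in both arms, the apparent effect moves toward no difference, and a baseline imbalance can appear as a treatment difference.

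A reader might go on to infer that a real effect will in fact be diluted, by roughly the amounts shown. The SAP does not support that: entry prevalence, re-documentation and event rates are all assumed, and with no entry ARDS the distortion is zero.

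Severity is low. The endpoint is exploratory. Under section 7.11 it is summarized only if primary and secondary results look meaningful. All analyses are descriptive (sections 7.1 and 7.2), and section 7.11.3.4 names no test. No primary or secondary result depends on it.

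**What to change.** Amend section 7.11.3.4, before database lock, to:

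1. State that ARDS present at baseline and unchanged is not an event, whatever the source. Section 7.12.1 already applies an onset-or-worsening condition to adverse events; extend the same idea to imaging and examination findings.
2. Derive a baseline ARDS flag from the available screening and baseline data, and tabulate it by arm with the section 7.7 summaries.
3. Report new-onset ARDS with numerator and denominator limited to patients without ARDS at baseline.
4. Report documented worsening separately, among patients with ARDS at baseline, against a criterion written down in advance. Do not use intubation as that criterion: it is already a primary endpoint (section 7.11.1.2).

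The cost is SAP wording and one derived flag. Screening imaging is optional, so some patients will have unknown baseline status; show them as a separate category. Denominators shrink, but the loss of precision is smaller than the harm from dilution in illustration 1. At b = 20% with s = 1, approximate power (two-sided 0.05, normal approximation) is 0.42 on the restricted 32 and 64 patients against 0.26 under the literal rule. Both figures are low, and they serve only to compare the two definitions.
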